## Appendix 2. ECOG Status Scores and Formulas

Status	Eastern Cooperative Oncology Group (ECOG) Performance Status**
0	Fully active, able to carry on all pre-disease performance without restriction.
1	Restricted in physically strenuous activity but ambulatory and able to carry out work of a light or sedentary nature, e.g., light housework, office work.
2	Ambulatory and capable of all self-care, but unable to carry out any work activities. Up and about more than 50% of waking hours.
3	Capable of only limited self-care, confined to bed or chair more than 50% of waking hours.
4	Completely disabled. Cannot carry on any self-care. Totally confined to bed or chair.
5	Dead.

Available at: [http://www.ecog.org/general/perf\\_stat.html](http://www.ecog.org/general/perf_stat.html). Accessed January 4, 2008.

## Cockcroft-Gault Equation

$(140\text{-Age}) * \text{Mass (in kg)}] \backslash [72 * \text{Serum creatinine (in mg/dL)}]$

\*If the patient is female, multiply the above by 0.85

## Appendix 3. Inhibitors and Inducers of CYP3A

Inhibitors of CYP3A are defined as follows. A comprehensive list of inhibitors can be found at the following website: <http://medicine.iupui.edu/clinpharm/ddis/table.aspx>. The general categorization into strong, moderate, and weak inhibitors according to the website is displayed below. Refer to [Section 6.2.1](#) on instructions for concomitant use of CYP3A inhibitors and inducers with ibrutinib.

Inhibitors of CYP3A	Inducers of CYP3A
Strong inhibitors:	
INDINAVIR	Carbamazepine
NELFINAVIR	Efavirenz
RITONAVIR	Nevirapine
CLARITHROMYCIN	Barbiturates
ITRACONAZOLE	Glucocorticoids
KETOCONAZOLE	Modafinil
NEFAZODONE	Oxcarbazepine
SAQUINAVIR	Phenobarbital
SUBOXONE	Phenytoin
TELITHROMYCIN	Pioglitazone
Moderate inhibitors:	Rifabutin
Aprepitant	Rifampin
Erythromycin	St. John's Wort
diltiazem	Troglitazone
Fluconazole	
grapefruit juice	
Seville orange juice	
Verapamil	
Weak inhibitors:	
Cimetidine	
All other inhibitors:	
Amiodarone	
NOT azithromycin	
Chloramphenicol	
Boceprevir	
Ciprofloxacin	
Delavirdine	
diethyl-dithiocarbamate	
Fluvoxamine	
Gestodene	
Imatinib	
Mibepradil	
Mifepristone	
Norfloxacin	
Norfluoxetine	
star fruit	
Telaprevir	
Troleandomycin	
Voriconazole	

Source: <http://medicine.iupui.edu/clinpharm/ddis/table.aspx>.

## Appendix 4. Response Criteria

### Revised response criteria for lymphoma

Response criteria	PET-CT-based response	CT-based response
Complete remission (CR)		
Lymph nodes and extralymphatic sites	Score 1, 2, or 3* with or without a residual mass on 5-PS**  No extralymphatic sites of disease	Target nodes/nodal masses must regress to $\leq 1.5$ cm in LD i
Non-measured lesion Organ enlargement New lesions Bone marrow	Not applicable Not applicable None No evidence of FDG-avid disease in marrow	Absent Regress to normal None Normal by morphology; if indeterminate, IHC negative
Partial remission (PR)		
Lymph nodes and extralymphatic sites	Score 4 or 5** with reduced uptake compared with baseline and residual mass(es) of any size	$\geq 50\%$ decrease in SPD of up to 6 target measurable nodes and extranodal sites
Organ enlargement New lesions Bone marrow	Not applicable  None Residual uptake higher than uptake in normal marrow but reduced compared with baseline (diffuse uptake compatible with reactive changes from chemotherapy allowed). If there are persistent focal changes in the marrow in the context of a nodal response, consideration should be given to further evaluation with MRI or biopsy, or an interval scan	Spleen must have regressed by $>50\%$ in length beyond normal None Not applicable
No response or stable disease (SD)		
Target nodes/nodal masses, extranodal lesions	No response: score 4 or 5 with no significant change in FDG uptake from baseline, at interim or end of treatment	Stable disease: $<50\%$ decrease from baseline in SPD of up to 6 dominant, measurable nodes and extranodal sites; no criteria for PD are met
Non-measured lesions Organ enlargement New lesions Bone marrow	Not applicable Not applicable None No change from baseline	No increase consistent with progression No increase consistent with progression None Not applicable

**Progressive disease (PD)**

Individual target nodes/nodal masses, extranodal lesions

Score 4, 5 with an increase in intensity of uptake from baseline and/or new FDG-avid foci consistent with lymphoma at interim or end of treatment assessment

An individual node must be abnormal with:

- LDi >1.5 cm
- Increase by  $\geq 50\%$  from PPD nadir

An increase in LDi or SDi from nadir

- 0.5 cm for lesions  $\leq 2$  cm
- 1.0 cm for lesions  $>2$  cm

In the setting of splenomegaly, the splenic length must increase by  $>50\%$  of the extent of its prior increase beyond baseline (e.g., a 15 cm spleen must increase to  $>16$  cm). If no prior splenomegaly, must increase by at least 2 cm from baseline

New or clear progression of pre-existing non-measured lesions

New FDG-avid foci consistent with lymphoma rather than another etiology, e.g. infection, inflammation. If uncertain regarding etiology of new lesions, biopsy or interval scan may be considered

New or recurrent splenomegaly

New lesions

Regrowth of previously resolved lesions

A new node  $>1.5$  cm in any axis  
A new extranodal site  $>1.0$  cm in any axis if less than 1.0 cm in any axis, its presence must be unequivocal and must be attributable to lymphoma

Assessable disease of any size unequivocally attributable to lymphoma

Bone marrow

New or recurrent FDG avid foci

New or recurrent involvement

## Deauville Criteria for PET Score

- 1 no uptake
- 2\* uptake <mediastinum
- 3\* uptake >mediastinum but <liver
- 4 Uptake moderately increased compared to the liver at any site.
- 5 Uptake markedly increased compared to the liver at any site or/and new sites of disease.

\* If mediastinal blood pool activity is equal or greater than liver then the uptake within the lesion should be compared with liver (lesion uptake less than liver=score 2; lesion uptake equal to liver=score 3).

Source: Report on the Second International Workshop on interim positron emission tomography in lymphoma held in Menton, France, 8-9 April 2010. Meignan M, Gallamini A, Haioun C, Polliack A. Leuk Lymphoma 51; 2010:2171-80.[\(33\)](#) Cheson et al. J Clin Oncol 32 2014

**Appendix 5****Barbara Ann Karmanos Cancer Institute****Data and Safety Monitoring (DSM) Report****PROTOCOL #:** \_\_\_\_\_**REPORT DATE:** \_\_\_\_\_

PROTOCOL TITLE					
ATTENDANCE					
PROTOCOL ACTIVITY SINCE LAST REPORT					
Accrual Goal:	Eligible:		Total number of AE's to date:		
Accrual to Date:	Ineligible (provide reason):				
Accrual Since Last Monthly Report:					
SPECIFICALLY FOR PHASE I TRIAL &/OR DOSE ESCALATING TRIALS:					
DOSE LEVEL	ACCRUAL				
1					
2					
3					
RECORD ALL GRADE 3, 4, AND 5 AE'S AND GROUP BY CTCAE CATEGORIES. RECORD THE DATE OF THE OCCURRENCE, ATTRIBUTION AND IF REPORTABLE TO THE IRB. SHADE THE ROWS OF THE AE'S THAT HAVE OCCURRED FOR THIS REPORT. ATTACH THE IRB REPORT FORM FOR THE REPORTABLE EVENTS THAT OCCURRED ON THIS REPORT.					
Pt. ID#	Category and type of adverse reaction	Date of Occurrence	Grade 	Attribution 	Reportable to IRB (Y/N) Yes with date

1. Grade: 1-Mild, 2-Moderate, 3- Severe, 4-Life-threatening, or 5- Death.

2. Attribution: 1-unrelated, 2 - unlikely, 3 - possibly, 4 - probably, or 5 - definitely

OFF TREATMENT  Provide reason [progression, death, toxicity, completed therapy, etc.].
--

PROTOCOL DEVIATIONS  Accidental or unintentional change from the protocol.
--

PROTOCOL AMENDMENTS  Include date submitted and approved by the IRB.
--

OTHER COMMENTS
-----------------------

Investigator Signature/Date:	Study Coordinator Signature/Date:
-------------------------------------	--

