#### **9.4.2. Safety Analysis**

Frequency of grade 3 or higher adverse events will be tabulated as will all grade 1 and 2 adverse events with frequency greater than 5%, e.g. occurring in 2 or more individuals.

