**Related:**

The AE is clearly related to use of the investigational product.

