#### 10.3.6.1 Major Hemorrhage

Major hemorrhage is defined as any of the following:

- Any treatment-emergent hemorrhagic adverse events of Grade 3 or higher\*. Any treatment-emergent serious adverse events of bleeding of any grade
- Any treatment-emergent central nervous system hemorrhage/hematoma of any grade

\*All hemorrhagic events requiring transfusion of red blood cells should be reported as grade 3 or higher AE per CTCAE v4.03.

Events meeting the definition of major hemorrhage will be captured as an event of special interest according to Section 10.3.6 above.

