### **11 STUDY ADMINISTRATION AND INVESTIGATOR OBLIGATIONS**

### **12 DATA AND SAFETY MONITORING**

1. Scheduled investigator meetings will be held monthly or more frequently depending on the activity of the protocol. These meetings will include the protocol investigators and research staff involved with the conduct of the protocol.
2. During these meetings the investigators will discuss:
  - Safety of protocol participants (adverse events and reporting)
  - Validity and integrity of the data (data completeness on case report forms and complete source documentation)
  - Enrollment rate relative to expectation of target accrual, (eligible and ineligible participants)
  - Retention of participants, adherence to the protocol and protocol deviations
  - Protocol amendments
3. In addition, Data and Safety Monitoring Reports (DSMR) of the research meetings will be completed by the Study Coordinator from each site and submitted to the Karmanos Data and Safety Monitoring Committee (DMSC) monthly for review. **(See Appendix 5)** The DSMC will review safety of study subjects and will recommend continuation or closure of

the study. The DSMC will review the safety data quarterly and will recommend termination if they judge the rate and severity of AEs to be unacceptable. The DSMC's recommendations will guide study conduct.

4. The Barbara Ann Karmanos Cancer Institute, Data and Safety Monitoring Committee (DSMC) is composed of medical providers, pharmacists and research staff and provides the primary oversight of data and safety monitoring for KCI Investigator-initiated trials.

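### A major hemorrhage of grade 1-2 in a single patient has no required line on the DSMC report form and no assured row in the safety table, although the protocol counts it as major at any grade.

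*Combined protocol and SAP*

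**What the plan says.** Section 10.3.6.1 defines major hemorrhage by three criteria. One depends on grade (grade 3 or higher). The other two do not: "Any treatment-emergent serious adverse events of bleeding of any grade" and "Any treatment-emergent central nervous system hemorrhage/hematoma of any grade". A footnote requires bleeds needing red-cell transfusion to be reported as grade 3 or higher. Seriousness in Section 10.1.2 rests on outcomes such as death or hospitalization, not on grade.

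Sections 10.3.6 and 10.3.7 send SAEs and AESIs to KCI and Pharmacyclics within 24 hours. They do not mention the DSMC.

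Section 12 says site reports are "submitted to the Karmanos Data and Safety Monitoring Committee (DMSC) monthly for review". Appendix 5 is that report. Its line-listing instruction is "RECORD ALL GRADE 3, 4, AND 5 AE'S AND GROUP BY CTCAE CATEGORIES". The columns are patient, type of event, date, grade, attribution and IRB reportability, with none for seriousness or AESI status. Lower grades enter only through "Total number of AE's to date", a bare count.

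Section 9.4.2 tabulates every event of grade 3 or higher, and "all grade 1 and 2 adverse events with frequency greater than 5%, e.g. occurring in 2 or more individuals". Section 9 plans no separate SAE, AESI or major hemorrhage table.

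**The concern.** The protocol singles out one event class and says that part of it matters at any grade. The two places where safety data are summarized then filter by grade, and the analysis filters by frequency as well. Neither filter exempts SAEs or AESIs. A site and an analyst who follow the text exactly can leave a protocol-defined major hemorrhage off both.

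Two things are at stake. The DSMC is asked to recommend termination on the rate and severity of adverse events, and Section 1.5.1 lists fatal and intracranial bleeding among the known risks of this drug. Safety and tolerability is also a secondary objective, so the final table could understate major hemorrhage and serious events.

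**Working it through.** **Inputs.** The planned total is 35 patients (Sections 3.1 and 9.5). The safety denominator is everyone who took any ibrutinib (Section 9.2), so up to 35. The cut-off for grade 1-2 events is above 5% (Section 9.4.2).

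**Step 1: the plan's own equivalence.** With k affected patients out of N, an event is tabulated when k/N > 0.05.

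- 1/35 = 2.86%: not tabulated.
- 2/35 = 5.71%: tabulated.
- With 31 patients: 1/31 = 3.23% (not tabulated) and 2/31 = 6.45% (tabulated).

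One patient exceeds 5% only when N is 19 or fewer, and two patients exceed it up to N = 39. Reading the cut-off as two or more individuals is therefore right for any N from 20 to 39.

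**Step 2: which major hemorrhages pass each filter.**

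| Event | Required line in Appendix 5 | Tabulated under 9.4.2 |
|---|---|---|
| Bleed of grade 3 or higher | Yes | Yes |
| Transfused bleed (reported as grade 3+) | Yes | Yes |
| Untransfused grade 1-2 serious or CNS bleed, two or more patients with the same term | No | Yes, but not marked as major |
| Untransfused grade 1-2 serious or CNS bleed, one patient | No | No |

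The last row is the gap. Any other grade 1-2 SAE seen in one patient is treated the same way.

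**Step 3: how often exactly one patient would be affected.** The documents give no rate for grade 1-2 major hemorrhage, so the per-patient rate p is an assumption and is shown over a range. With n = 35:

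P(at least one) = 1 - (1 - p)^35

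P(exactly one) = 35 × p × (1 - p)^34

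| Assumed p | P(at least one) | P(exactly one) | Share with exactly one, given any |
|---|---|---|---|
| 1% | 0.297 | 0.249 | 84% |
| 2% | 0.507 | 0.352 | 70% |
| 3% | 0.656 | 0.373 | 57% |
| 5% | 0.834 | 0.306 | 37% |

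For example, at 3%: 1 - 0.97^35 = 0.656, 35 × 0.03 × 0.97^34 = 0.373, and 0.373/0.656 = 0.57.

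**Step 4: limits of step 3.** The calculation treats all such bleeds as one category. If the table is built by event term, two patients with different terms each stand at 1/35 and both are dropped, so omission could be more frequent. In the other direction, if other patients have the same term without meeting the definition, the term gets a row, but nothing in it identifies a major hemorrhage.

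**The case against.** The strongest reply is that these events are already handled quickly and that the gap is small. Much of that stands. Every SAE and AESI reaches KCI, the institution whose committee is the DSMC, within 24 hours, and the synopsis says all grade 1 and 2 events are collected. The footnote on transfused bleeds moves those events to grade 3 or higher. Few of the remaining grade 1-2 bleeds would meet the seriousness criteria, and one isolated low-grade event is unlikely on its own to change a DSMC judgement.

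A reader might go further and infer that the DSMC cannot see these events. The documents do not support that. Section 12 also gives the committee a quarterly review of safety data whose content is not specified, and monthly investigator meetings discuss adverse events without a grade limit. The form's instruction is a minimum, not a ban: its legend runs from grade 1 to grade 5 and it has a free-text comments box. Likewise, Section 9.4.2 does not forbid an additional SAE listing.

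A reader might also infer that the form's attribution codes, "Attribution: 1-unrelated, 2 - unlikely, 3 - possibly, 4 - probably, or 5 - definitely", damage the safety analysis because Section 10.1.4 has only four levels. The mismatch is real but minor. The top level in 10.1.4 is defined as "The AE is clearly related to use of the investigational product", which sits naturally with the form's highest code, and Section 9.4.2 tabulates nothing by attribution.

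What remains is that none of these routes requires a grade 1-2 AESI or SAE to be shown to the DSMC or given a row in the table.

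**Conclusion.** The point holds in a narrow form. The stated filters conflict with a stated any-grade definition, so an untransfused grade 1-2 serious or CNS bleed in one patient, or any other single grade 1-2 SAE, has no required place on the DSMC form and falls below the table's cut-off. This is possible omission from two summaries. It is not loss of data and not certain concealment from the committee.

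Only the contrast between 2.9% and 5.7% rests on the documents. The 84% to 37% range depends on assumed rates of 1% to 5%, 35 treated patients, and treating these bleeds as one category. No single figure within it should be quoted as the expected effect. The primary endpoint and the sample size are untouched. It is a cheap improvement to safety oversight and reporting that is worth making.

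**What to change.** In Appendix 5, change the instruction so that sites record all grade 3-5 events plus all SAEs and all AESIs of any grade, and add two columns: serious (Y/N) and AESI (Y/N).

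In Section 9.4.2, add one sentence: all SAEs and all major hemorrhage AESIs will be tabulated regardless of grade or frequency, in addition to the current rules. A single grade 1-2 major hemorrhage would then appear as 1/35 (2.9%).

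While the form is open, its attribution codes can be aligned with the four levels of Section 10.1.4. This is housekeeping and not part of the point.

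The cost is a form revision, one added sentence and a few more rows per report. No new data are needed, because these events are already collected and expedited, and no treatment rule changes.

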## **Appendix 6**

**See attached diary**

## Appendix 7. Child-Pugh Score

Measure	1 point	2 points	3 points
Total bilirubin, $\mu$ mol/L (mg/dL)	<34 (<2)	34-50 (2-3)	>50 (>3)
Serum albumin, g/L (g/dL)	>35 (>3.5)	28-35 (2.8-3.5)	<28 (<2.8)
PT INR	<1.7	1.71-2.30	>2.30
Ascites	None	Mild	Moderate to Severe
Hepatic encephalopathy	None	Grade I-II (or suppressed with medication)	Grade III-IV (or refractory)

Points	Class
5-6	A
7-9	B
10-15	C

Source:

